Outcome measures: Venous patency, blood flow direction, peak reflux velocity, circumferences (C1, C2) at the end of each segment length (L), BMI, VRT, Genomic DNA blood test, Estriol (E3) levels, progesterone serum levels, outcome of quality of life.

Population: 70 Random pregnant women.

Eligibility: Pregnant women aged between 18-47 years old.

Duration: 1 year, follow up period will be conducted at the end of first, second and third trimester and three months after giving birth.

1 Introduction

1.1 Background

Varicose veins (VV) are the early sign of Chronic venous insufficiency (CVI) which are characterised by abnormal tortuosity and dilatation of superficial veins of lower limb extremities (Naoum *et al.*, 2007). Symptoms of VV are variable and depend on the stage and severity of disease. In early stages, symptoms of VV include pain, leg heaviness and mild swelling (Adhikari *et al.*, 2000). As the disease advances, symptoms include skin changes such as pigmentation, lipodermatosclerosis and ulceration (Kendler *et al.*, 2010; Shadrina *et al.*, 2018). Pregnancy is an established risk factor for the development of VV (Ismail *et al.*, 2016). Three main hypotheses for this observation have been proposed. First, it was hypothesised that increased size of gravid uterus during pregnancy may result in increased venous pressure on iliac veins resulting in a disruption of lower limb venous outflow (Mashiah *et al.*, 1991). However, VV may develop in the first trimester before the onset of these mechanical factors (Dindelli *et al.*, 1993). Secondly, pregnancy results in an increased blood volume which may lead to elevated pressure in lower limb vasculature (Ismail *et al.*, 2016). Both theories suggest that high pressures may result in venous valve impairment (Bergan *et al.*, 2006). Thirdly, VV in pregnant women were found to be associated with increased estrogen and progesterone levels (Mashiah *et al.*, 1991; Ortega, Asunsolo, Alvarez-Rocha, *et al.*, 2018). Estrogen hormone elevates coagulation protein levels which cause thrombosis. Additionally, estrogen dilates venous valves due to its role in relaxation and releasing the chains between collagen fibers. On the other hand, progesterone prevents smooth muscle contraction which therefore increases valvular insufficiency due to vasodilation which causes lack of connection between two valves (Ropacka-Lesiak, *et al.*, 2012). Moreover, large number of studies have discussed the associated risk factors that contribute to VV development. However, there are lack of studies that consider VV risk factors and pathophysiology in pregnant women. Understanding the aetiology of VV in pregnancy may allow us to better identify those at risk and manage this risk accordingly.

1.2 Rationale for current study

Regardless of the underlying pathophysiological cause, VV may have a negative social impact on patient's life and negative economic impact on health care budget. VV if left untreated can progress to late stages of chronic venous insufficiency (CVI) which include skin changes and ulceration (Adhikari *et al.*, 2000). Ulcers lower patient's quality of life and may result in social isolation, depression, reduce the ability to work and patients will be dependent on others (Evans *et al.*, 1994; Cesarone *et al.*, 2002). Furthermore, venous disease is costly to manage for healthcare service. For example, the cost of managing chronic wounds caused by ulcers in the UK National Health Service (NHS) during 2005 to 2006 was estimated from 2.3 to 3.1 billion pounds which was equivalent to 3% of total UK health care budget (Posnett, J. and Franks, 2007). Interestingly, the cost was increased between 2012 to 2013 when cost was estimated at 5.3 billions of pounds annually which consume 4% of the total health UK health care budget (Guest *et al.*, 2015).

1.3 Research hypothesis:

The development of post-partum chronic venous insufficiency is predictable and caused by both mechanical and hormonal factors.

2 Study aim and objectives:

The primary aim of this proposed study is to better understand the pathophysiology of VV in pregnant women. This aim will be achieved by meeting the following objectives:

Primary objective:

To develop an antenatal test to predict the risk of developing VV post-partum.

Secondary aims:

1. To evaluate mechanical factors causing VV in pregnancy
2. To evaluate hormonal factors causing VV in pregnancy.
3. To determine whether lower limb pain during pregnancy is related to changes in lower limb venous system.

3 Methods

3.1 Study design:

A prospective longitudinal study will be undertaken to assess the development of VV among pregnant women. This study will follow up patients for one year, starting by following up pregnant women from the first trimester of pregnancy to the end of the second and third trimester. Last follow up will be performed three months after giving birth. Consequently, this proposed prospective study will be conducting four follow ups for each participant.

3.2 Recruiting pregnant women in their first trimester:

Initially, patients will be approached by a member of the direct care team in the Maternity outpatients' departments in the following hospitals: West Middlesex hospital, Queen Charlotte's and Chelsea hospital and St Mary's hospital. This will be managed by experienced research professionals in the area of vascular surgery. If a patient is prepared to discuss their potential role in this research, then the researchers will discuss the study and recruitment details at the patient's convenience. Recruitment is completely voluntary and will not affect their routine care, this will be made clear during the discussion regarding the research, and again during the consenting process. Time will be made available for any questions and for the patient to consider recruitment in their own time. Patients will be required to consent before any study-related procedures are carried out. Then her personal identifiable data will be coded and pseudonymised.

The recruited patient will be interviewed to obtain clinical information that is essential for robust analysis. This clinical information will include standard demographic form which will be used for all patients in each follow up in order to record and gather important information which represents the composition of the target population. Gathered data will include patients' details; patients name, day of visit, hospital name, ID number, date of birth. Furthermore, this demographic form will record potential risk factors which may associate with VV development such as race, number of

pregnancies, family history of venous disease, BMI which include weight and height, occupational factors, smoking, alcohol consumption and diet. Any complications arising from pregnancy will be also recorded (appendix 12.1). Finally, this proposed study will only record fetal weight in second and third trimester to correlate increased fetal weight with potential venous pathology.

First, patients will be asked to fill the demographic form then will be asked to stand on a scale to measure the weight. Height will be recorded by bringing the horizontal measure down to rest on the top of the participants head. Following this, patient will be asked to sit while measurements are recorded in a relevant source data sheet.

Next, the patient will be asked to stand on a step facing the sonographer to assess the incidence of varicose veins using Duplex ultrasound (DUS) and vector flow imaging (VFI). While patient is standing, Truncated cone tool will be performed immediately by measuring leg circumferences in each segments of each limb to produce accurate measurements of lower limbs volume. Following this, patient will be asked to sit on a chair for perform Iliac vein compression test (venous outflow function) using photoplethysmography (PPG) technique. Finally, patient's quality of life assessment will be evaluated by using Aberdeen Varicose Veins Questionnaire (AVVQ) check list (Klem, Sybrandy and Wittens, 2009). Thereafter, the patient will be thanked for their participation and excused.

Clinical Laboratory tests will be managed and performed by experienced research professionals in the area of vascular surgery. Four appointments will be arranged for each patient to investigate DNA genomic testing and Estriol (E3) and progesterone hormonal testing. First appointment during first trimester will include both genomic DNA and hormonal blood tests. The three remaining appointments in the second trimester, third trimester and three months after giving birth will include hormonal blood samples only. Patients will be entitled to exit the study at any time without providing a reason, this is clearly stated on our information sheet and consent form. Verbal consent will be requested before all follow-up ultrasound scans.

Researchers will ensure that demographic data, ultrasound data, lower limb volume and iliac vein compression measurements, histopathological results and quality of life

assessment results will be collected and stored in such a way that confidentiality is preserved. All data will be pseudonymised by replacing names with research codes and by keeping any identifying information separate from the main dataset.

The data will be analysed with the help of the Imperial College statistics department. The results of this study may be presented at local, national or international meetings or submitted for publication in a peer-reviewed journal. From a patient's perspective, all data will be pseudonymous before the statistical analysis phase of the study and plans to publish the results of the study are made clear in our patient information sheet. Data and all appropriate documentation will be stored for a minimum of 10 years after the completion of the study, including the follow-up period.

3.3 Study group protocol

3.3.1 Protocol for gathering patient's demographic information

Recruited pregnant women will be asked to take a seat to fill a demographic form which contains patients' personal details (name, date of birth, hospital number, date of visit and hospital name) and other varicose veins risk factors (see appendix 12.2), filling this form may take up to 5 min. Following this, BMI risk factor will be calculated by measuring patients' weight and height.

First, weight scale will be placed flat on the level ground. Scale will be ensured is at zero before commencing. Patient will be asked to remove heavy clothes and empty pockets. Preferably, shoes should be removed. Following this, patient will be asked to stand, and weight reading will be recorded when it has stabilised. Weight will be recorded in kilograms and to the nearest 0.1 kg. Second, height will be measured by asking the patient to remove their shoes and stand unsupported with their back to the vertical scale. Patients feet should be parallel to each other while standing, toes pointing forward and soles flat on the floor. Also, patient should be ensured that she is standing as tall as possible looking straight ahead. Horizontal measure will be brought down to rest on the top of the participants head. The measurement on the vertical scale to the nearest millimetres will be recorded on the relevant source data

sheet. Measuring weight and height will take 5 min, which means collecting patients' demographic factors will take 10 min in total.

3.3.2 Protocol for Duplex ultrasound scan (DUS)

All recruited pregnant women be scanned by duplex ultrasound scan (DUS) to investigate the evidence of VV. The examination will be bi lateral for each patient. The patient will be asked to remove their clothes to expose the lower limb from groin to ankle. Patient will be examined standing to evaluate valves competency against gravity. This is because veins are more dilated while standing which make it easier and more accurate to assess. This examination is considered intimate; therefore, a chaperone will be offered. The scan duration will take 30-45 min and patients may sometimes feel dizzy during the examination. To overcome this issue, patients will be asked to sit and take a rest during the examination.

There are two main techniques which will be applied to all venous segments. Firstly, B mode technique. B mode technique will be used to evaluate vein patency in transverse scan plane by observing the compressibility of veins to rule out any possibility of blood clots. Secondly, Spectral (Pulse wave) doppler technique will be used to evaluate venous flow characteristics (phasicity, spontaneity and direction flow) in longitudinal scan plane by applying manual distal augmentation to assess the reflux duration. All scans and measurements will be performed on SuperSonic Imagine's Aixplorer ® ultrasound system. Following this, 9 MHz linear ultrasound probe will be placed on the patient skin over the venous blood vessel to be scanned, with the use of coupling gel between the skin and the probe.

The scan will start by evaluating the deep and superficial veins system. Firstly, deep veins will be assessed by scanning the Common femoral vein (CFV) at the groin for patency and flow. Any abnormality in CFV indicates iliac vein obstruction therefore iliac veins and inferior vena cava should be examined. The examination will be continued by scanning the length of femoral vein (FV) (proximal to distal), popliteal vein and calf veins. Any thrombus or incompetence (Incompetent veins are defined as a reflux time more than 0.5 seconds) will be recorded.

Secondly, superficial venous veins will be assessed after completing the deep venous system examination. This will be achieved by starting again from the groin to evaluate the patency and competency of both sapheno-femoral junction and the entire length of long saphenous vein (LSV). This will be coupled with assessing all venous perforators and branches. LSV diameters will be recorded in case of any required future treatment. After that, examining the sapheno-popliteal junction and short saphenous vein (SSV) will be performed by repositioning the patient to assess patency and competency. Therefore, VV found in LSV or SSV should be evaluated to detect linked sources of reflux such as reflux in perforators. Finally, all recordings will be saved and entered in the research database for analysis.

3.3.3 Protocol for Vector flow imaging (VFI):

Ultrasound machines currently use conventional Spectral (Pulse wave) doppler to assess the reflux duration in varicose veins protocols. Although spectral doppler is widely used, however, it is limited in detecting accurate peak reflux velocity estimation due to two main reasons. Firstly, its angle-dependency which means it can only detect blood velocities along the direction of ultrasound beam. Secondly, due to the anatomical location of lower extremities superficial veins. To overcome this issue, Vector flow imaging (VFI) which is a new ultrasound technique can be used. This technique is a beam steering and angle independent technique which can detect accurate peak reflux velocity estimation. VFI has been used recently in evaluating the velocity of lower limb veins and obtained promising results (Bechsgaard *et al.*, 2016, 2017).

While the recruited patient is standing, she will be scanned by VFI which is based on transverse oscillation (TO) ultrasound method. VFI software will be installed in the same SuperSonic Imagine's Aixplorer® ultrasound scanner. Again, 9 MHz linear ultrasound probe will be placed in longitudinal scan plane on the patient's skin over the venous blood vessels to be scanned, with the use of coupling gel between the skin and the probe. The scan will start by emitting conventional Pulse wave doppler estimation. Following this, by using special estimator and changing apodization in receive, both axial and transverse velocity components will be found at the same time.

Then, blood flow will appear in a colour box, a colour wheel will indicate the direction of the blood flow and overlaid arrows in the colour box will make the interpretation of flow direction and magnitude easier. Finally, the patient will be asked to rest and take a seat. All recordings will be saved and entered in the research database for analysis.

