7.2 Study outcome measures

	Intervention/procedure	Outcome measures
Primary outcome	DUS	
 • Patency • Blood flow direction(antegrade/retrograde) • Peak reflux velocity
Secondary outcomes	VFI	
 • Patency • Blood flow direction(antegrade/retrograde) • Peak reflux velocity
	Truncated cone tool	
 • C1 • C2 • h
	PPG	Severity of venous reflux by measuring Venous refiling time (VRT) (Abnormal less than 20 sec)
	Genomic blood test	Genomic DNA
	Hormonal Blood test	Estroil (E3) levels, progesterone serum levels
	AVVQ questionnaire	Outcome of quality of life (0-100). 0 least severe (good quality of life), 100 most severe (low quality of life).

8 Statistics and data analysis

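### The primary DUS outcome includes a velocity for which the protocol calls Doppler limited, and none of its three measures applies the protocol's own criterion for an incompetent vein

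*Combined protocol and SAP*

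**What the plan says.** All places are in the combined protocol and SAP.

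- **Section 7.2** gives DUS as the only source of the primary outcome, with three measures: patency, "Blood flow direction(antegrade/retrograde" and "Peak reflux velocity". The same three measures taken by VFI are secondary.
- **The study summary** opens its outcome list with "Venous patency, blood flow direction, peak reflux velocity, circumferences (C1, C2) at the end of each segment length (L), BMI, VRT". Reflux time and incompetence do not appear in that list.
- **Section 3.3.3** says that spectral Doppler is what scanners conventionally use for reflux duration, but that "it is limited in detecting accurate peak reflux velocity estimation due to two main reasons". The first reason is "its angle-dependency which means it can only detect blood velocities along the direction of ultrasound beam"; the second is where the superficial leg veins lie. VFI is introduced to overcome this, as an "angle independent technique which can detect accurate peak reflux velocity estimation".
- **Section 3.3.2** uses Doppler in the DUS scan to judge flow characteristics, including direction, "by applying manual distal augmentation to assess the reflux duration". It adds: "Incompetent veins are defined as a reflux time more than 0.5 seconds". Incompetence is to be recorded. Patency is judged by B-mode compression, to exclude clot.
- **Section 8.2** compares patency and peak reflux *time* between VFI and DUS by descriptive statistics. It then models patency and peak reflux *velocity* by mixed logistic regression.

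**The concern.** Two choices in 7.2 pull against the methods sections. The primary velocity is assigned to the technique that the protocol describes as limited for it, while the technique introduced to measure it accurately is secondary. And the quantity for which the DUS procedure is set up, reflux duration with a stated limit for incompetence, is not a named outcome.

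The primary objective in section 2 is an antenatal test that predicts varicose veins post-partum. A predictive test needs a defined event. If no primary measure says when a vein is incompetent, the choice among direction, velocity and duration stays open until the data are in hand, and the main conclusion could depend on it.

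**Working it through.** **1. Does any primary measure identify an incompetent vein?** Take the three DUS measures in 7.2 against the criterion in 3.3.2 (reflux time over 0.5 s):

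- *Patency.* Compression excludes clot; it does not test valve competence. The 0.5 s criterion is not used.
- *Flow direction.* Antegrade or retrograde, with no duration limit in 7.2. The text does not say whether reverse flow of 0.5 s or less counts as retrograde, although such a vein is not incompetent under 3.3.2. The criterion is not used.
- *Peak reflux velocity.* A continuous quantity with no cut-off anywhere in the document. The criterion is not used.

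Result: 0 of 3.

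**2. Does the analysis plan repair this?** Section 8.2 names reflux time once, descriptively, for DUS against VFI. The regression that follows takes velocity. A logistic model needs a categorical outcome, and no cut-off for velocity is given. Section 8.3 compares direction and velocity between DUS and VFI by kappa. Neither section applies 0.5 s.

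**3. Does the sample size name the event?** Section 8.1 gives an exact two-sided 5% binomial test, proportions 0.25 and 0.10, N = 70, power 91.27%. With at most 2.5% in each tail, the test rejects at 10 or fewer events (P = 0.0220 under 0.25; 11 or fewer would give 0.0439) or at 26 or more. The power is P(X ≤ 10 | n = 70, p = 0.10) = 0.9127, which reproduces the stated figure. That arithmetic is sound and does not itself bear on this point. It shows only that one yes/no result per woman is needed. Section 8.1 does not say which, and 7.2 has no rule that yields one.

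**4. How sensitive is a Doppler velocity to angle?** Reading / true velocity = cos(true angle) / cos(assumed angle). The documents give no angle; 60 degrees and errors of 5 and 10 degrees are assumptions.

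- True 65: cos 65 / cos 60 = 0.845, about −15%
- True 55: cos 55 / cos 60 = 1.147, about +15%
- True 70: cos 70 / cos 60 = 0.684, about −32%
- True 50: cos 50 / cos 60 = 1.286, about +29%

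These are errors in a single reading. They illustrate why the protocol mentions angle and measure no effect on any planned analysis. The point stands without them.

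**The case against.** The strongest reply is that the plan is less bare than 7.2 suggests. Reflux time does appear in 8.2 under the analysis of primary and secondary outcomes, and 3.3.2 says incompetence will be recorded. This stands: the data will exist, and it would be wrong to say reflux time is absent from the plan. But a descriptive comparison of two devices does not make it an outcome, and the 0.5 s limit is attached to nothing that is analysed.

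Three stronger readings are tempting and are not supported:

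- *That Doppler cannot measure the velocity, or is unreliable.* Section 3.3.3 says limited. Patency, by B-mode compression, is not affected by Doppler angle at all.
- *That brief reverse flow will be scored retrograde.* The documents are silent. Direction and duration are assessed in the same manoeuvre, and a sonographer may well apply 0.5 s when calling direction. It is an ambiguity, not a stated rule.
- *That error in the primary measures weakens every association with hormones, limb volume and risk factors.* The risk-factor tests in 8.3 use varicose veins as the outcome. Section 8.2 compares limb volumes with each other across visits, and relates hormone levels to the next visit and to varicose vein development. The documents do not say that varicose vein status is derived from velocity or direction. Velocity enters the logistic model and the DUS-VFI kappa; direction is named only in that kappa.

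It is also fair to say that the 0.5 s definition sits in the deep-vein paragraph of 3.3.2. The superficial-vein text speaks of competency without a threshold, so applying the limit there has to be stated.

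**Conclusion.** The point holds as an inconsistency between 7.2 and sections 3.3.2, 3.3.3 and 8.2. The primary velocity rests on the technique that the protocol calls limited for it, and none of the three primary measures, as written, identifies an incompetent vein. The only DUS criterion that does so is outside the outcome list. This rests on the documents' text and on no outside figure. How much any result would change cannot be derived from the documents, and it should not be inferred that the predictive test is already known to carry misclassified outcomes.

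**What to change.** In 7.2, the study summary and 8.2:

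1. Make DUS reflux duration the primary reflux measure. Define incompetence as more than 0.5 s, as in 3.3.2, and also keep the time as a continuous value.
2. State that the definition applies to superficial as well as deep segments.
3. Reduce it to one result per woman at the post-partum visit, for example any incompetent superficial segment in either leg. Section 8.1 should then say whether its 0.25 and 0.10 refer to that event.
4. Move peak reflux velocity to a secondary outcome measured by VFI, with DUS velocity as comparator.
5. Keep flow direction only as a secondary DUS-VFI agreement measure, which matches the kappa in 8.3.
6. Use reflux time and reflux velocity consistently in 8.2, and name which one each analysis takes.

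Cost: an amendment that changes the stated primary outcome, to be made before analysis. No new measurement is needed, since section 7 already schedules the DUS scan at all four visits and 3.3.2 already assesses reflux duration in it.
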